1. H_{03}
2. H_{02}
3. H_{01}

The 3 hypotheses will be tested one-sided on a 2.5% significance level. The testing procedure will stop as soon as one of the hypotheses cannot be rejected following the pre-specified order. Due to this sequential order of tests an adjustment for a potential type-I-error due inflation due to the multiple testing is not required.

An estimate for the difference in CUA lesions during the specified periods compared to the baseline period will be reported, together with one-sided p-values. In addition, 95% CI and two-sided p-values will be presented to allow for comparison with the two-sided secondary and tertiary analyses.

Robustness Analyses

The robustness of the primary analysis model will be evaluated by repeating the analysis using generalized model assuming a negative binomial distribution.

In order to evaluate the robustness of the assumption that missing data are observed at random (MAR), the primary analysis will be repeated applying a pattern mixture model. If missingness can be considered MAR (e.g. MRI missing for technical reasons), data will be imputed by multiple imputation from post-baseline data while if considered not missing at random (MNAR) (e.g., drop-out due to lack of efficacy), data will be imputed from baseline data. The propensity score method based on CUA lesion count during the baseline period, age, and EDSS will be applied.

8.5.3 Analysis of Secondary and Tertiary Endpoints

Analysis comparing continuous secondary and tertiary endpoints measured repeatedly at specific time points to baseline will be undertaken using similar techniques to those outlined for the primary analysis while taking the within-subject correlation into account where appropriate. Linear regression modelling assumes that outcomes are normally distributed. Appropriate transformations (such as square root or log transform) may be used to achieve normality. Alternatively, nonparametric methods may be applied.

Annualized relapse rate will be evaluated using a Poisson regression model with count of relapses as dependent variable and with age and EDSS as covariates. The log of time under

observation (in days) will be the offset variable in the model. Categorical endpoints will be analyzed by logistic regression.

Safety endpoints will be summarized descriptively, providing detail of the frequency, type, severity and outcome of the events.

Other outcomes will be summarized descriptively.

CCI

CCI

8.6 Interim and Additional Planned Analyses

As the primary analysis is available after all subjects have completed the 6-month assessment, this analysis will be conducted at this stage. The full dataset up to and including the 6-month assessment will be subject to appropriate data cleaning for all variables involved in the primary analysis, consisting of post-entry validation checks and assessing the data for outliers, for example.

Interim analysis at this stage will also consider descriptive summaries of other outcomes. Data cleaning will be undertaken on all data involved in interim reporting.

9 Ethical and Regulatory Aspects

9.1 Responsibilities of the Investigator

The Investigator is responsible for the conduct of the trial at the site and will ensure that the trial is performed in accordance with this protocol, the ethical principles outlined in the Declaration of Helsinki, ICH GCP, and any other applicable regulations. The Investigator must ensure that only subjects who have given informed consent are included in the trial.

9.2 Subject Information and Informed Consent

An unconditional prerequisite for each subject prior to participation in the trial is written informed consent, which must be given before any trial-related activities are carried out. Adequate information must therefore be given to the subject by the Investigator or an appropriate designee (if local regulations permit) before informed consent is obtained.

A subject information sheet must be prepared in the local language in accordance with ICH GCP and will be provided by the Sponsor for the purpose of obtaining informed consent. In addition to providing this written information to a potential subject, the Investigator or a designate will inform the subject verbally of all pertinent aspects of the trial, using language chosen so that the information can be fully and readily understood by laypersons. The subject will be given sufficient time to read the information and the opportunity to ask questions and to request additional information and clarification.

If permitted by national regulations, a person other than the Investigator may inform the subject about the trial and sign the ICF, as above.

After the information is provided by the Investigator, the ICF must be signed and dated by the subject and the Investigator.

The signed and dated declaration of informed consent will remain at the Investigator's site, and must be safely archived so that the forms can be retrieved at any time for monitoring, auditing and inspection purposes. A copy of the signed and dated information and ICF should be provided to the subject prior to participation.

Whenever important new information becomes available that may be relevant to informed consent, the Investigator will revise the subject information sheet and any other written information to be provided to the subjects and submit them to the IRB for review and opinion. Using the approved revised subject information sheet and other written information, The Investigator will explain the changes to the previous version to each trial subject and obtain new written consent for continued participation in the trial. The subject will be given sufficient time to read the information and the opportunity to ask questions and to request additional information and clarification about the changes.

9.3 Subject Identification and Privacy

A unique number will be assigned to each subject, immediately after informed consent has been obtained. This number will serve as the subject's identifier in the trial as well as in the clinical trial database. All subject data collected in the trial will be stored under the appropriate subject number. Only the Investigator will be able to link trial data to an individual subject via an identification list kept at the site. For each subject, original medical data will be accessible for the purposes of source data verification by the Monitor, audits and regulatory inspections, but subject confidentiality will be strictly maintained.

Data protection and privacy regulations will be observed in capturing, forwarding, processing, and storing subject data. Subjects will be informed accordingly, and will be requested to give their consent on data handling procedures in accordance with national regulations.

After the end of the study, samples will be stored at a Sponsor's designated biorepository under the supervision of Sponsor.

9.4 Emergency Medical Support and Subject Card

Subjects will be provided with Emergency Medical Support cards supplied by the Sponsor for use during trial participation in order to provide clinical trial subjects with a way of identifying themselves as participating in a clinical trial and to give health care providers access to any information about this participation that may be needed to determine the course of medical treatment for the subject.

The first point of contact for all emergencies will be the clinical trial Investigator caring for the affected subject. The Investigator agrees to provide his or her emergency contact information on the card for this purpose. If the Investigator is available when an event occurs, they will answer any questions. Any subsequent action will follow the standard process established for Investigators.

In cases where the Investigator is not available, the Sponsor provides the appropriate means to contact a Sponsor physician. This includes the provision of a 24-hour contact number at a call center, whereby the health care providers will be given access to the appropriate Sponsor physician to assist with the medical emergency and to provide support for the management of the subject concerned.

9.5 Clinical Trial Insurance and Compensation to Subjects

Insurance coverage will be provided for each country participating to the trial. Insurance conditions shall meet good local standards, as applicable.

9.6 Independent Ethics Committee or Institutional Review Board

Prior to commencement of the trial at a given site, this clinical trial protocol will be submitted together with its associated documents (for example, IMP Dossier, Subject Information and ICF, as per national and local regulations) to the responsible IEC or IRB for its favorable opinion or approval, which will be filed in the Investigator Site File. A copy will be filed in the Sponsor Trial Master File at (Sponsor or designated organization).

The IEC or IRB will be asked to document the date of the meeting at which the favorable opinion or approval was given and the members and voting members present. Written evidence of favorable opinion or approval that clearly identifies the trial, the clinical trial protocol version and the Subject Information and ICF version reviewed should be provided. Where possible, copies of the meeting minutes should be obtained.

Amendments to this clinical trial protocol will also be submitted to the concerned IEC or IRB, before implementation of substantial changes (see Section 10.5). Relevant safety information will be submitted to the IEC or IRB during the course of the trial in accordance with national regulations and requirements.

9.7 Health Authorities

The clinical trial protocol and any applicable documentation (for example, IMP Dossier, Subject Information and ICF) will be submitted or notified to the Health Authorities in accordance with all local and national regulations for each site.

10 Trial Management

10.1 Case Report Form Handling

Refer to the Manual of Operations for eCRF handling guidelines.

The main purpose of the eCRF is to obtain data required by the clinical trial protocol in a complete, accurate, legible and timely. The data in the eCRF should be consistent with the relevant source documents.

The Investigator or designee is responsible for ensuring that the data collected in the course of this trial is accurate and documented appropriately on all applicable forms. They will then be processed, evaluated, and stored in anonymous form in accordance with applicable data protection regulations. The Investigator must ensure that the eCRFs and any other associated documents forwarded to Sponsor or its designated organization contain no mention of any subject names.

The data will be entered into a validated database. The Sponsor or its designee will be responsible for data processing, in accordance with the Sponsor's data management procedures. Database lock will occur once quality control and quality assurance procedures have been completed. PDF files of the eCRFs will be provided to the Investigators at the completion of the trial.

10.2 Source Data and Subject Files

The Investigator must keep a file (medical file, original medical records) on paper or electronically for every subject in the trial. It must be possible to identify each subject by using this subject file. This file will contain the demographic and medical information for the subject listed below and should be as complete as possible.

- Subject's full name, date of birth, sex, height, weight
- Medical history and concomitant diseases
- Prior and concomitant therapies (including changes during the trial)
- Trial identification, that is, the Sponsor trial number for this clinical trial, and subject number
- Dates for entry into the trial (informed consent) and visits to the site
- Any medical examinations and clinical findings predefined in this clinical trial protocol
- All AEs

- Date that the subject left the trial including any reason for early withdrawal from the trial or IMP (if applicable).

All documents containing source data must be filed, including, but not limited to computed tomography (CT) or MRI scan images, ECG recordings, and laboratory results. Such documents must bear the subject number and the date of the procedure. If possible, this information should be printed by the instrument used to perform the assessment or measurement. As necessary, medical evaluation of such records should be performed; all evaluations should be documented, signed, and dated by the Investigator.

Electronic subject files will be printed whenever the Monitor performs source data verification. Printouts must be signed and dated by the Investigator, countersigned by the Monitor and kept in a safe place at the site.

10.3 Investigator Site File and Archiving

Upon initiation of the trial, the Investigator will be provided with an Investigator Site File containing all necessary trial documents, which will be completed throughout the trial and updated as necessary. The file must be available for review by the Monitor, during Sponsor audits and for inspection by Health Authorities during and after the trial, and must be safely archived for at least 15 years (or longer, per local requirements or as otherwise notified by the Sponsor) after the end of the trial. The documents to be archived include the Subject Identification List and the signed subject ICFs. If archiving of the Investigator Site File is no longer possible at the site, the Investigator must notify the Sponsor/designee.

All original subject files (medical records) must be stored at the site (hospital, research institute, or practice) for the longest possible time permitted by the applicable regulations, and/or as per ICH GCP guidelines, whichever is longer. In any case, the Investigator should ensure that no destruction of medical records is performed without the written approval of the Sponsor.

10.4 Monitoring, Quality Assurance and Inspection by Health Authorities

This trial will be monitored in accordance with the ICH GCP, and any other applicable regulations. The site Monitor will perform calls and visits to the trial site at regular intervals.

The clinical trial protocol, each step of the data capture procedure, and the handling of the data, including the final clinical trial report, will be subject to independent quality assurance activities. Audits may be conducted at any time during or after the trial to ensure the validity and integrity of the trial data. Representatives of the Quality Assurance unit from the Sponsor or a designated organization, as well as Health Authorities, must be permitted to access all trial documents and other materials at the site, including the Investigator Site File, the completed CRFs, all IMP and IMP accountability records, and the original medical records or files for each subject.

10.5 Changes to the Clinical Trial Protocol

Changes to the clinical trial protocol will be documented in writing. Substantive amendments will usually require submission to the Health Authorities and to the relevant IEC/IRB for approval or favorable opinion. In such cases, the amendment will be implemented only after approval or favorable opinion has been obtained.

Minor (nonsubstantial) protocol amendments, including administrative changes, will be filed by the Sponsor and at the site. They will be submitted to the relevant IEC/IRB or to Health Authorities only where requested by pertinent regulations. Any amendment that could affect the subject's agreement to participate in the trial requires additional informed consent prior to implementation following the process as described in Section 9.2.

10.6 Clinical Trial Report and Publication Policy

10.6.1 Clinical Trial Report

After completion of the trial, a clinical trial report will be written by the Sponsor in consultation with the Coordinating Investigator following the guidance in ICH Topic E3.

Assessments	Pre-baseline Screening	Baseline	Month 1	Month 2	Month 3	Month 6	Month 12	Month 14	Month 15	Month 18	Early termination/ Month 24
Visit windows	Up to -3 months	+7 days	±7 days	±7 days	±7 days	±7 days	±7 days	±7 days	±7 days	±7 days	±7 days
Informed consent ¹	X										
Demographics, medical history	X										
Inclusion/exclusion criteria	X	X									
Weight ² / Cladribine Tablets dispensed		X	X				X				
IRT contacted	X	X	X				X				
Trial medication administered at site		X	X				X				
Physical examination ³	X	X				X	X			X	X
Lymphocyte count ⁴	X			X		X	X	X		X	X
Serology ⁵	X						X				
TB (active, latent) ⁶	X						X				
Urine pregnancy test ⁷	X	X					X				
MRI	X	X	X	X	X	X	X		X	X	X
CCI											
Disability (EDSS/KFS)	X	X				X	X			X	X
Disability (9HPT)	X	X				X	X			X	X
Disability (T25FW)	X	X				X	X			X	X
Cognition (SDMT)		X				X	X			X	X
Relapse count ⁹		X					X				X
Adverse events, concomitant medications and procedures ¹⁰	X	X	X	X	X	X	X	X	X	X	X
Collection and review of subject diary ¹⁰		X	X	X	X	X	X	X	X	X	X

Abbreviations: 9HPT=9-Hole Peg Test; EDSS=Expanded Disability Status Scale; KFS= Kurtzke Functional System; IRT=interactive response technology; MRI=magnetic resonance imaging; SDMT=Symbol Digit Modalities Test; T25FW=Timed 25-Foot Walk; TB=tuberculosis

1. Informed Consent should be obtained prior to any trial-specific assessments are undertaken
2. Weight to be measured before each treatment course for calculating appropriate dose of cladribine
3. Includes vital signs (blood pressure, heart rate, body temperature)

4. To be done at a local laboratory. If the lymphocyte count at screening is done before 4 weeks from Baseline, it should be repeated within 4 weeks of Baseline. Lymphocyte count should be (i) normal before initiating cladribine in year 1, (ii) at least 800 cells/mm³ before initiating in year 2 (iii) checked at 2 and 6 months after start of treatment in each treatment year. If necessary, the treatment course in year 2 can be delayed for up to 6 months to allow for recovery of lymphocytes. If this recovery takes more than 6 months, cladribine treatment should be terminated
5. To be done at a local laboratory. Serology test for HIV, Hepatitis C, Hepatitis B to be done at screening and at month 12, and varicella to be done at screening. Subjects with a negative varicella serology will be included after 4 to 6 weeks of receipt of varicella vaccination.
6. Screening test for active and latent TB will be done as per local guideline (to be done at a local laboratory)
7. To be done at a local laboratory. As per local guideline, urine or serum pregnancy test may be done
8. CCI [REDACTED]
9. Captured in subject diary when at home
10. May be captured by the trial site personnel and/or trial nurse into eCRF

CCI

CCI

[figure not shown]

CCI

CCI

CCI

CCI

CCI

CCI

CCI

CCI

CCI

CCI

CCI

CCI

CCI

A large black rectangular redaction box covering the majority of the page content.

CCI

A large black rectangular redaction box covering the majority of the page content.

CCI

A large black rectangular redaction box covering the majority of the page content.

CCI

CCI

CCI

CCI

A large black rectangular redaction box covering the majority of the page's content.

CCI

A large black rectangular redaction box covering the majority of the page's content.

CCI

A large black rectangular redaction box covering the majority of the page's content.

12.6 Appendix 6: 9-Hole Peg Test (9HPT)

General Information:

- The 9HPT should be conducted with the dominant arm first
- One practice trial (per arm) should be provided prior to timing the test
- Timing should be performed with a stopwatch and recorded in seconds
- The stop watch is started when the patient touches the first peg
- The stop watch is stopped when the patient places the last peg in the container

Set-up (Mathiowetz et al, 1985):

- A square board with 9 holes,
 - holes are spaced 3.2 cm (1.25 inches) apart
 - each hole is 1.3 cm (0.5 inches) deep
- 9 wooden pegs should be .64 cm (.25 inches) in diameter and 3.2 cm (1.25 inches) long
- A container that is constructed from .7 cm (.25 inches) of plywood, sides are attached (13 cm x 13 cm) using nails and glue
- The peg board should have a mechanism to decrease slippage. Self-adhesive bathtub appliques were used in the trial
- The pegboard should be placed in front of the patient, with the container holding the pegs on the side of the dominant hand

Patient Instructions (Mathiowetz et al, 1985):

- The instructions should be provided while the activity is demonstrated
- The patient's dominant arm is tested first
- Instruct the patient to:
 - "Pick up the pegs one at a time, using your right (or left) hand only and put them into the holes in any order until the holes are all filled. Then remove the pegs one at a time and return them to the container. Stabilize the peg board with your left (or right) hand. This is a practice test. See how fast you can put all the pegs in and take them out again. Are you ready? Go!"

- After the patient performs the practice trial, instruct the patient:
 - “This will be the actual test. The instructions are the same. Work as quickly as you can. Are you ready? Go!” (Start the stop watch when the patient touches the first peg.)
 - While the patient is performing the test say “Faster”
 - When the patient places the last peg on the board, instruct the patient “Out again...faster.”
 - Stop the stop watch when the last peg hits the container.
- Place the container on the opposite side of the pegboard and repeat the instructions with the non-dominant hand.

Dominant Hand (circle one): Right Left Time to complete the test in seconds:

Date: _____ Dominant Hand: _____ Non-Dominant Hand: _____

Date: _____ Dominant Hand: _____ Non-Dominant Hand: _____

Date: _____ Dominant Hand: _____ Non-Dominant Hand: _____

Date: _____ Dominant Hand: _____ Non-Dominant Hand: _____

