14.3.13 No Evidence of Progression or Active Disease

No Evidence of Progression or Active Disease (NEPAD) is a composite measure, evolution of NEDA-3, including relapses and different measurements of disability progression and MRI activity.

NEPAD at Month 24 is defined as the composite endpoint of NEDA-3 and the absence of:

CCI [REDACTED]

CCI [REDACTED]

- 20% progression on T25-FW,
- 20% progression on 9HPT,

during the Treatment Period.

20% confirmed T25FW progression

20% confirmed progression on T25FW is defined by an increase of at least 20% from T25FW Baseline that is sustained over a 6-month time Period.

The increase will be defined as sustained when it occurs on two post-Baseline Visits, which are at least 166 days (6 months * 30 -14 days Visit Window) apart and no score at any other Visit including unscheduled Visits in between is less than the defined increase.

The occurrence of a 20% confirmed T25FW progression is defined as:

- Yes: sustained T25FW progression that started during the Treatment Period.
- No: at least 2 post-Baseline T25FW assessments that are 166 (or more) days apart are available and no sustained T25FW progression that started during the Treatment Period.
- Unknown: Otherwise.

Only T25FW assessments with the same assistance devices as at Baseline will be analyzed. T25FW trials which couldn't be finished by the subjects will be imputed with 3 minutes (see Section 14.3.17).

20% confirmed 9HPT progression

20% confirmed progression on 9HPT is defined by an increase of at least 20% from 9HPT Baseline that is sustained over a 6-month time Period.

The increase will be defined as sustained when it occurs on two post-Baseline Visits, which are at least 166 days (6 months * 30 - 14 days Visit Window) apart and no score at any other Visit including unscheduled Visits in between is less than the defined increase.

The occurrence of a 20% confirmed 9HPT progression is defined as:

- Yes: sustained 9HPT progression that started during the Treatment Period.
- No: at least 2 post-Baseline 9HPT assessments that are 166 (or more) days apart and no sustained 9HPT progression that started during the Treatment Period.
- Unknown: Otherwise.

Analysis of NEPAD

NEPAD will be analyzed with a logistic regression with adjusting factors age (in years) and EDSS at Baseline (≤ 3 , >3).

Analysis (Analysis Set)	Derivation	Statistical Analysis Methods	Missing data handling
Tertiary endpoint: NEPAD at 24 months			

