14.3.16 Changes in level of disability as measured by 9HPT

The 9HPT should be completed at Baseline and then at Month 6, 12, 18, and 24 Visit to measure the level of disability over time. The subjects have to stick 9 pegs in 9 holes and place them back. That will be done twice for each hand. The mean of the 4 stop times will be analyzed. At least one stop time must be recorded, otherwise, the Visit will be considered as missing. Details of the 9HPT are included in the appendix of the study protocol.

Analysis (Analysis Set)	Derivation	Statistical Analysis Methods	Missing data handling
Tertiary endpoint: Changes in level of disability as measured by 9HPT at Month 6, 12, 18, and 24 Visit compared to Baseline			
Tertiary (FAS)	Change from Baseline in mean time of the 9HPT to the Month i Visit, where i= 6, 12, 18, and 24.	Mixed-effects linear model for repeated measures, same as in Tertiary Analysis for Change from Baseline in CUA lesion count (see Section 14.3.1)	Same as in Tertiary Analysis for Change from Baseline in CUA lesion count (see Section 14.3.1)

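### Protocol Appendix 6 yields two timed 9HPT runs per visit but SAP 14.3.16 averages four stop times; define one visit score and match it by hand to Baseline

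*Protocol*

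**What the plan says.** **Protocol Appendix 6 (Section 12.6).** The general instructions read "One practice trial (per arm) should be provided prior to timing the test". After the practice run the subject is told "This will be the actual test. The instructions are the same. Work as quickly as you can", and only there does the script say to start the stopwatch. The container is then moved to the other side and the examiner is to "repeat the instructions with the non-dominant hand". The form, under "Time to complete the test in seconds", has one dominant and one non-dominant entry on each dated line.

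**Protocol 7.3.2.3** schedules the 9HPT at Pre-Baseline, Baseline and Months 6, 12, 18 and 24. It gives no number of timed runs.

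**SAP 14.3.16** states "That will be done twice for each hand. The mean of the 4 stop times will be analyzed". One recorded stop time is enough for a visit not to count as missing. The section closes with "Details of the 9HPT are included in the appendix of the study protocol". The endpoint is change from Baseline in mean time at Months 6, 12, 18 and 24.

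**SAP 14.3.13** defines a NEPAD component: "20% confirmed progression on 9HPT is defined by an increase of at least 20% from 9HPT Baseline", sustained on two post-Baseline visits at least 166 days apart. It does not say how the 9HPT score is built.

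**SAP Section 7**, which lists changes to the planned analyses, does not mention the 9HPT.

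**The concern.** The SAP takes its test procedure from an appendix that does not produce the input the SAP asks for. Whoever programs the endpoint has to guess whether the score is a mean of two or four times, and whether any practice time belongs in it.

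A change score or percentage increase means something only if Baseline and follow-up are built alike. The SAP does not require this. With the one-stop-time rule, a visit may contribute one hand or two, and one run per hand or more, and still be set against whatever was available at Baseline. For the T25FW the documents are tighter: Protocol 7.3.2.4 and SAP 14.3.17 agree on two walks, and the SAP analyses only walks done with the same assistance device as at Baseline. The 9HPT has no such safeguard.

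**Working it through.** **1. Stop times per visit**

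| Source | Timed runs per hand | Hands | Stop times |
|---|---|---|---|
| Protocol Appendix 6 | 1 | 2 | 1 × 2 = 2 |
| SAP 14.3.16 | 2 | 2 | 2 × 2 = 4 |

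The SAP's 4 does not follow from Appendix 6. It is reached only if a second timed run per hand was added that the appendix does not describe, or if the two practice runs were also timed (2 + 2 = 4). The four dated lines on the form do not settle this: each has its own date and one entry per hand.

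**2. What the one-stop-time rule allows**

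Let the faster hand take time D and the slower hand D(1 + h). The documents give no value for h. I assume that SAP 14.3.13 uses the 14.3.16 score.

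- Baseline mean of both hands: D(1 + h/2).
- Follow-up with only the slower hand and no true change: ratio (1 + h)/(1 + h/2), an apparent worsening.
- Follow-up with only the faster hand and no true change: ratio 1/(1 + h/2), an apparent improvement.
- The slower hand alone reaches the 20% threshold when (1 + h)/(1 + h/2) = 1.2, so 1 + h = 1.2 + 0.6h and h = 0.2/0.4 = 0.5.

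A slower hand taking 50% longer would therefore give a 20% increase with no change in function. For this to become confirmed progression, the rise would have to hold at a second visit at least 166 days away with no lower score between. Smaller differences shift the change scores in the same way.

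An incomplete set of four also matters. With two times for one hand and one for the other, the plain mean is (2D + N)/3, where N is the other hand's time, and the hands are no longer equally weighted.

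**3. Practice runs, only if their times are recorded and averaged in**

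Suppose the practice run is slower than the timed run by a fraction p0 at Baseline and p1 at follow-up. Each score is inflated by 1 + p/2.

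- Apparent change with unchanged function: (1 + p1/2)/(1 + p0/2) − 1.
- True worsening needed to read 20%: 1.20 × (1 + p0/2)/(1 + p1/2) − 1.

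Assumed ranges, not from the documents: p0 of 5–10%, p1 of 0–4%.

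| p0 | p1 | Apparent change | True worsening needed |
|---|---|---|---|
| 5% | 4% | 1.02/1.025 − 1 = −0.5% | 1.20 × 1.025/1.02 − 1 = 20.6% |
| 5% | 0% | 1/1.025 − 1 = −2.4% | 1.20 × 1.025 − 1 = 23.0% |
| 10% | 4% | 1.02/1.05 − 1 = −2.9% | 1.20 × 1.05/1.02 − 1 = 23.5% |
| 10% | 0% | 1/1.05 − 1 = −4.8% | 1.20 × 1.05 − 1 = 26.0% |

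If p0 = p1 the factors cancel and a true 20% reads as 20.0%. If follow-up practice is relatively slower, the sign reverses: with p0 = 5% and p1 = 20%, a true 20% reads as 1.20 × 1.10/1.025 − 1 = 28.8%.

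**The case against.** The best defence is that the SAP may describe the fields actually collected. It is later than the protocol, since it cites specifications from 2021. Appendix 6 reads like a generic instrument description: its set-up is credited to a 1985 norms paper, and its form has four dated lines for a schedule of six 9HPT visits. Section 7 of the SAP also says in general terms that tertiary endpoint wording was aligned with a data transfer specification. This is possible but not shown. The data transfer documents in the SAP's reference list concern MRI and biomarker data, and the SAP still sends the reader to Appendix 6. What stands is that the appendix, not the SAP, may be the text to correct.

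Three stronger readings are tempting, and the documents do not support them:

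- **That no score can be computed.** The one-stop-time rule lets a score be formed from two values. Only the stated mean of four does not follow from Appendix 6.
- **That practice runs enter the score and hide worsening.** Appendix 6 places practice before timing, and nothing says practice times are recorded. Even if they were, equal effects cancel and the direction can reverse. A Pre-Baseline 9HPT also precedes Baseline, which should lessen any excess there.
- **That some sites supply two values and others four.** Sites work from the protocol, and Protocol 10.1 points to the Manual of Operations for eCRF handling. Nothing shows sites following the SAP's wording.

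It is also fair to say that little depends on this. Protocol 8.5.1 makes every analysis other than the primary one exploratory, and the 20% rule is one NEPAD component that needs confirmation.

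**Conclusion.** The conflict is confirmed by counting: 2 stop times under Protocol Appendix 6, 4 under SAP 14.3.16, with no explanation in SAP Section 7. The SAP also leaves open comparisons of unlike scores between Baseline and follow-up. Both affect the 9HPT change analysis and, on the assumption that 14.3.13 uses the same score, the 9HPT component of NEPAD.

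The effect on results is unknown, because the eCRF is not among the documents. The practice-run figures (−0.5% to −4.8% apparent change; 20.6% to 26.0% true worsening needed) hold only if practice times were recorded and averaged in, and only under the assumed 5–10% and 0–4%. They show what exclusion guards against, not a bias known to exist. The primary and secondary endpoints are untouched. Severity is minor.

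**What to change.** 1. Check how many timed runs per hand the eCRF holds, and correct whichever text is wrong. With one per hand, SAP 14.3.16 should average two times. With two per hand, Appendix 6 should describe both after the practice run. Valid timed runs should not be discarded to fit either text.
2. State in SAP 14.3.16 that practice runs are excluded.
3. Average within hand first, then across hands, so that a missing run does not alter the weight of each hand.
4. Compute change from Baseline, and the 20% rule in SAP 14.3.13, only from the same hand or hands at Baseline and follow-up, and name in 14.3.13 the score it uses.
5. Add a rule for visits with only one hand recorded, for example comparing with the same hand at Baseline or treating the visit as missing.

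The cost is a few sentences and one change to the derivation program. A few visits with one hand recorded may drop out or need the special rule, although the SAP as written keeps them.
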